6.3.7. Electrocardiogram

ECG examination in this trial will be performed in 12 leads (I, II, III, aVR, aVL, aVF, V1 - V6) at Visits 0, 2, 4.

The ECG will be recorded for a time sufficient for evaluation (up to 10 seconds) after the patient has been at rest for a minimum of 10 minutes.

The HR will be measured and an opinion will be given as to whether the patient's ECG is normal, clinically significant or clinically insignificant.

At Visit 0, if data are available for a patient from an ECG examination performed within 48 hours prior to the patient's inclusion in the trial, these can be used to assess the patient's status and eligibility for inclusion/non-inclusion. A repeat ECG on Visit 0 is not required in this case.

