8.3. AE recording and reporting

Adverse events (AEs)

The protocol provides for the recording of all AEs that occur to the patient after the first administration of the trial therapy and until the end of the patient's participation in the trial.

During screening, information about medical adverse events will be attributed to the patient's medical history (pre-existing/concomitant conditions).

The planned trial will record all deviations in the health status of patients (based on the results of physical examination, laboratory and instrumental methods of investigation) from the data obtained at the Screening and from the accepted reference values.

After obtaining the necessary information, the investigating physician will categorise the patient's condition as 'normal', 'clinically insignificant abnormalities' or 'clinically significant abnormalities'. In case the abnormalities detected during the trial have not been previously reported, or there is an aggravation of the patient's condition vs. the data obtained at Screening, the detected abnormalities will be classified as AEs.

If the abnormalities detected during the trial have been recorded at Screening and there is no significant negative trend in the reasonable opinion of the investigator, the detected abnormalities will be classified as clinically insignificant abnormalities (CIA).

All detected abnormalities, irrespective of whether they are attributed to AE or CIA, will be analysed when reporting the results of the clinical trial.

An adverse event is defined as any adverse change in the health status of a patient or subject of a clinical trial/trial to whom a medicinal product has been administered, irrespective of the causal relationship with its use.

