All data obtained from the trial are subject to analysis. The final analysis of efficacy parameters will be performed after the clinical part of the trial is completed and the electronic database is finalised. If errors are identified in the electronic database prior to finalisation that cannot be resolved after the completion of patient participation in the trial, the statistical analysis of the data will include an analysis of the sensitivity of the resulting parameters to the presence of questionable data.

10. Safety analysis

Safety indicators as well as their changes will be presented using descriptive statistics by visit and therapy group. On trial visits, qualitative (dichotomous) measures will be compared between groups on the basis of Pearson's χ^2 test, if the frequency of a feature in at least one subgroup is 5 or less, Fisher's exact test (or Fisher-Freeman-Galton test for tables of arbitrary dimensionality).

The dynamics of quantitative safety indicators relative to baseline values will be evaluated and compared with each other using ANOVA analysis of variance with repeated measures. This method allows to simultaneously check the presence of statistically significant dynamics (at least one mean value in one time point differs from the rest), as well as to compare the dynamics and ranges of values of the indicator when receiving the compared preparations. In case of inappropriate use of parametric methods, similar analysis of changes in the distributions of

Version 1.0 of 12.11.2021

*Protocol-Specific Version for Protocol #PHS-
APIS-004-MEX-SOL-TAV. version 1.3 dated
07.06.2021*

CONFIDENTIAL

page 30 of 58

Plan for statistical analysis of efficacy and safety parameters

indicators during therapy will be carried out using non-parametric analogues - Friedman test and Wilcoxon sign rank test, and intergroup comparisons of changes - using the Wilcoxon-Mann-Whitney test.

The number and proportion of patients with reported adverse events after the first dose of the investigational product will be tabulated by therapeutic group. Descriptive statistics for adverse events will also be tabulated, taking into account severity, action taken and outcome.

The safety analyses will descriptively present the values of laboratory parameters as well as their changes from baseline values. In addition, clinically significant and nonsignificant deviations of laboratory values by visit will be tabulated by therapeutic group.

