Safety assessment will be carried out based on the analysis of the frequency of occurrence of all adverse events, dynamics of laboratory and instrumental parameters.

AEs are recorded after the first use of the drug until the patient completes the trial and are tracked throughout the trial until they are resolved/stabilised.

Frequency tables with data on discontinuation of therapy or changes in therapy parameters due to AEs will be presented.

Pre- and post-trial data will be compared to assess safety parameters.

All data will be analyzed on the safety population. Regardless of the reason for trial termination, data from all included patients will be included in the safety analyses of the trial therapy.

Adverse event (AE) is any adverse change in the health status of a patient or subject of a clinical trial to whom a medicinal (investigational) product has been administered, regardless of the causal relationship with its use.

Serious adverse event (SAE) - any adverse medical event that, regardless of the dose of the medicinal product, has resulted in death, is life threatening, requires hospitalization or its prolongation, has resulted in permanent or significant disability or impairment, is a congenital anomaly or birth defect or other medically significant event.

Adverse reaction (AR) - unintentional adverse body reaction associated with the use of a medicinal product/investigational product, suggesting at least a possible relationship with the use of a suspected medicinal product/investigational product.

Unexpected adverse reaction (UAE) - an adverse reaction, the nature, severity or outcome of which does not correspond to the information in the current instructions for medical use of the medicinal product or in the investigator's leaflet for an unregistered medicinal product.

Serious unexpected adverse reaction (SUAR) - an unexpected adverse reaction that is characterized by features of a SAE.

The parameters of the AE/SAE will be estimated as follows:

Severity of AEs:

The investigator assesses the severity of an adverse event according to the Common Terminology Criteria for Adverse Events (CTCAE) current version at the time of the trial. If an adverse event cannot be classified according to the CTCAE criteria, the Investigator will select the closest description of the severity of the adverse event from those given in the classification based on personal clinical experience:

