indicator ¹³	Visit 0	Visit 2	Visit 3	Visit 4	Dynamics to Visit 0		Visit 0	Visit 2	Visit 3	Visit 4	Dynamics to Visit 0	
					Abs.	%					Abs.	%
N												
Mean												
Median												
Min												
Max												
Qi												
Q3												
SD												
CV												
Comparison of drugs (statistical test ¹⁴) (p-value)												
Indicator span diagram/ indicator scatter diagram or indicator trend diagram												

Table 11. Safety performance assessment results: repeated measures analysis of variance (template)

Safety Indicator/Investigational Product	SS	DF	MS	F	p
Intercept					
Investigational Product					
Error					
Visit					
Visit*Dru					
Error					

Table 12. Results of safety indicators assessment: non-parametric repeated measures analysis of variance (Friedman test, template)

Investigational Product					
Indicator					
Visit	Average rank	Sum of ranks	Mean	SD	p
Visit 1					
...					

¹³ SBP, DBP, HR, RR, body temperature.

¹⁴ T-test for independent samples or Mann-Whitney test depending on the type of distribution of the indicator

Version 1.0 of 12.11.2021

**Plan for statistical analysis of efficacy and safety parameters***Table 13. Frequency analysis of safety performance outcome assessment (template)*

Investigational Product		Mexitol®			Placebo		
		Visit 0	Visit 2	Visit 4	Visit 0	Visit 2	Visit 4
Indicator 1							
Normal	Abs.						
	%						
Deviation	Abs.						
	%						
	%						
Comparison of groups (statistical criterion ¹⁵)							
p-level							
Indicator 2							
...							

Table 14. Frequency analysis of the safety outcome measure score (clinical significance, template)

Investigational Product		Mexitol®			Placebo		
		Visit 0	Visit 2	Visit 4	Visit 0	Visit 2	Visit 4
Indicator 1							
Deviation is clinically significant	Abs.						
	%						
Deviation is clinically insignificant	Abs.						
	%						
	%						
Comparison of groups (statistical criterion ¹⁶)							
p-level							
Indicator 2							

¹⁵ Pearson's χ^2 criterion or Fisher's exact test¹⁶ Pearson's χ^2 criterion or Fisher's exact test

Plan for statistical analysis of efficacy and safety parameters

Table 15. Statistical analysis of ECG (template)

Investigational Product		Mexidol®			Placebo		
		Visit 0	Visit 2	Visit 4	Visit 0	Visit 2	Visit 4
Normal	Abs.						
	%						
Deviation	Abs.						
	%						
	%						
Comparison of groups (statistical criterion ¹⁷)							
p-level							

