Table 16. Statistical analysis of physical examination parameters (outcome measure, template)

Investigational Product		Mexidol®				Placebo			
		Visit 0	Visit 2	Visit 3	Visit 4	Visit 0	Visit 2	Visit 3	Visit 4
Indicator 1									
Normal	Abs.								
	%								
Deviation	Abs.								
	%								
	%								
Comparison of groups (statistical criterion ¹⁸)									
p-level									
Indicator 2									
...									

Table 17. Distribution of patients by gender (template)

Gender		Mexidol®		Placebo	
Female	Abs.				
	%				
Male	Abs.				

¹⁷ Pearson's χ^2 criterion or Fisher's exact test

¹⁸ Pearson's χ^2 criterion or Fisher's exact test

Version 1.0 of 12.11.2021

Plan for statistical analysis of efficacy and safety parameters

	%	
Differences between	Pearson 's χ^2 criterion	
groups		

Table 18. Baseline patient characteristics (template)

Indicator ¹⁹	Mexitol®	Placebo
N		
Mean		
Median		
Min		
Max		
Qi		
Q3		
SD		
CV		
Comparison of groups	Statistical criterion ²⁰ , p-value	
Range diagram		Scatter diagram

Table 19. Total number of AEs (template)

AE	After administration of	
	Mexitol®	Placebo
Total number of AEs	Abs.	
Number of patients with detected AEs	Abs.	
	%	

Table 20. Relative risk of AEs (template)

Presence of adverse events in patients	Investigational Product	
	Mexitol®	Placebo
Identified	Abs.	
	%	
Not identified	Abs.	
	%	
Differences between preparations	Pearson 's χ^2 criterion or Fisher's exact test	
Relative risk of AEs [95% CI]		

¹⁹ Age, height, body weight or BMI

²⁰ T-test for independent samples or Mann-Whitney test depending on the type of distribution of the indicator

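### SAP Tables 15 and 16 compare ECG and physical-examination findings only as Normal versus Deviation at each visit, dropping the recorded clinical-significance rating and any patient-level shift from Visit 0

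*Protocol*

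**What the plan says.** **What is recorded.** ECGs are taken at Visits 0, 2 and 4. Under Protocol 6.3.7, for each one "an opinion will be given as to whether the patient's ECG is normal, clinically significant or clinically insignificant". Protocol 8.3, covering physical-examination, laboratory and instrumental results together, says that "the investigating physician will categorise the patient's condition as 'normal', 'clinically insignificant abnormalities' or 'clinically significant abnormalities". Protocol 6.3.4 lists the organ systems examined but does not say that each system receives its own three-level rating.

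**What is tabulated.** SAP Table 15 has two rows, Normal and Deviation, by arm at Visits 0, 2 and 4. SAP Table 16 has the same two rows for each examination indicator at Visits 0, 2, 3 and 4. Both compare the arms by Pearson's chi-square or Fisher's exact test. Neither has a significance row or cross-classifies a later visit against the patient's own Visit 0 result.

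**What the SAP text adds.** Section 10 promises that "clinically significant and nonsignificant deviations of laboratory values by visit will be tabulated by therapeutic group", which names laboratory values only. It also says in general terms that "Safety indicators as well as their changes will be presented using descriptive statistics by visit and therapy group" and that "Pre- and post-trial data will be compared to assess safety parameters". It assigns no method to categorical ECG or examination findings. SAP Table 14 is a clinical-significance template at Visits 0, 2 and 4 for unnamed indicators.

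**The concern.** The safety question for an ECG or an examination is whether new clinically important abnormalities arise more often on one arm. A Normal/Deviation count at a visit answers a different question: how many patients have any abnormality then, including those they brought into the trial. Some baseline ECG abnormality is plausible in patients aged 40 to 75 with acute stroke, although the documents give no rate.

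Two kinds of information are lost. The grade of the finding disappears, so insignificant and significant findings are counted alike. The patient's own starting point also drops out of the comparison: a Visit 0 column shows the arm total at entry, not which patients changed. At stake is the sensitivity of the two tables dedicated to these data, which Protocol 8.1 lists as safety evidence alongside AE reports.

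**Working it through.** **Structural check (no assumed rates).** Follow one patient's ECG through Table 15.

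| Visit 0 rating | Visit 2 rating | Table 15 row at Visit 0 | Table 15 row at Visit 2 |
|---|---|---|---|
| Normal | Clinically significant | Normal | Deviation |
| Clinically insignificant | Clinically significant | Deviation | Deviation |

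The second patient has worsened in the way that matters and the table does not register it.

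**Dilution.** Let b be the share with any deviation at Visit 0, equal in both arms and persisting, and q the rate of new clinically significant findings, independent of baseline status. The share in the Deviation row at a later visit is

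P = b + (1 − b)q,

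so the arm difference is (1 − b)(q₁ − q₀). The true difference is multiplied by 1 − b.

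**Inputs.**
- From the documents: 304 randomised 1:1 (Protocol 9.1 and 4.3.2), so 152 per arm; threshold p < 0.05 (SAP 9); Fisher's test when a subgroup frequency is 5 or less, otherwise chi-square (SAP 10).
- Assumed: q₀ = 2%, q₁ = 9%; b from 30% to 80%; two-sided tests, because the SAP does not state sidedness for safety; an ECG for all 152 per arm.

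The plan states no power for any safety test, so there is no figure of its own to reproduce.

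**Results for q = 2% v 9%** (true difference 7 points). Analysed directly, power is about 72%.

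| b | Deviation, placebo | Deviation, active | Difference | Power in Table 15 |
|---|---|---|---|---|
| 30% | 0.30 + 0.70 × 0.02 = 31.4% | 0.30 + 0.70 × 0.09 = 36.3% | 4.9 points | 15% |
| 40% | 41.2% | 45.4% | 4.2 points | 12% |
| 60% | 60.8% | 63.6% | 2.8 points | 8% |
| 80% | 80.4% | 81.8% | 1.4 points | 6% |

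**Other assumed rates, 152 per arm.**
- 2% v 10%: direct power 84% (chi-square) or 81% (Fisher). Table 15 gives 25%, 18%, 10%, 7% and 4% at b = 20%, 30%, 50%, 70% and 90%.
- 5% v 15%: direct power 83% or 80%. Table 15 gives 34%, 24%, 14%, 8% and 5% at the same values of b.

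**Limits of the direct analysis.** Protocol 9.1 allows for 304 falling to 228 protocol completers, which is 114 per arm. With 114 ECGs per arm, direct power for 2% v 9% drops from 72% to about 57%. For a smaller excess of 2% v 5% with 152 per arm it is about 18.5%.

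**The case against.** A reader might infer that new significant findings are hidden from the whole safety analysis, that these two tables are the only between-arm tests of such findings, and that baseline is ignored. The documents do not support any of these.

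- **AE route.** Protocol 8.3 classifies abnormalities that are new, or worse than at Screening, as AEs, which is a baseline-referenced rule. AEs are then compared between arms (Protocol 9.7.3): overall with a relative risk (SAP Table 20), by severity and seriousness (Tables 21 and 26) and by MedDRA preferred term (Table 31). This stands as real mitigation. It is not a full substitute. For an abnormality already recorded at Screening, escalation turns on the investigator's opinion that there is a significant negative trend. The comparisons are either over all AEs or split by term, and Table 33 lists system organ class without a test, so nothing pools ECG findings.
- **Table 14.** It names no indicators, and its visits match the ECG schedule, so ECG may have been intended there. But the SAP text mentions only laboratory values, ECG has its own table, and Table 14 has no shift from Visit 0. It also lacks the Visit 3 column that physical examination needs.
- **Baseline.** Visit 0 is displayed, and change and pre/post comparison are promised in general terms. What is missing is patient-level use of baseline.
- **Nervous-system row.** With entry NIHSS of 9 to 15, essentially every patient is in Deviation at Visit 0, so that row of Table 16 can show recovery but not worsening. It would be wrong to conclude that neurological worsening goes unexamined: change in NIHSS is compared between arms (SAP Table 5).
- **Bias.** Randomisation keeps the Table 15 and 16 comparisons fair between arms. The loss is in sensitivity.
- **Data for Table 16.** The documents do not show a significance rating for each body system, so that part of the remedy must be conditional.

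**Conclusion.** The point holds for Tables 15 and 16 as laid out. They discard a recorded clinical-significance rating and make no patient-level comparison with Visit 0, so they cannot separate new significant findings from abnormalities present at entry. The structural part needs no assumed rate.

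The size is illustrative. About 72% power falling to between 15% and 6% rests on assumed rates of 2% v 9%, on 30% to 80% abnormal at entry, on those abnormalities persisting, on independence from baseline status, and on no missing ECGs. None of the rates is in the documents. The direction does not depend on the rates chosen: under the persistence and independence assumptions, the arm difference shrinks by the factor 1 − b.

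This is a correctable loss of sensitivity in two tables, partly offset by AE reporting. It does not show that the trial would miss a safety signal altogether.

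**What to change.** - **Table 15 (ECG).** Show the three recorded levels and add a shift table by arm from Visit 0 to Visit 2 and from Visit 0 to Visit 4. Make the between-arm comparison, at each of those visits, the proportion of patients whose ECG is clinically significant and was not at Visit 0, among patients with an ECG at that visit.
- **Table 16 (physical examination).** Do the same at Visits 2, 3 and 4 where the significance rating is recorded per system. Where it is not, compare new Deviation since Visit 0.
- **Table 14.** State which indicators it covers. Naming ECG there would restore the rating but not the shift from baseline.

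The cost is SAP template wording and minor programming. The ECG part uses ratings the protocol already collects. For Table 16, first confirm what the eCRF captures per system; the fallback needs only the Normal/Deviation result already planned.

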6.3.8. Laboratory tests

The list of analysed indicators of laboratory tests is presented in Table 6.1.

Table 6.1. List of laboratory tests.

Laboratory tests to assess safety			Serological tests/other laboratory tests
Complete blood count	Biochemical blood test	Clinical urinalysis	
Erythrocyte sedimentation rate (ESR).	ALT	Urine protein.	Syphilis ¹
Haematocrit (Hct).	AST	Urine glucose.	Hepatitis B ¹
Haemoglobin (Hb).	Glucose	Urine erythrocytes.	Hepatitis C ¹
Red blood cell count.	Creatinine	Urine leukocytes.	HIV ₁
Platelet count.	Urea	Urine pH	Pregnancy test for women with preserved reproductive potential
White blood cell count.	Total protein	Bacteria in the urine sediment.	
Leucocytic formula: neutrophils: segmented neutrophils, bacilli (in relative and absolute units); eosinophils (in relative and absolute units); basophils (in relative and absolute units); monocytes (in relative and absolute	Triglycerides	Squamous epithelium in the urine sediment.	SARS-CoV-2 IgM antibody rapid test
	Total cholesterol		

¹ Results obtained within 48 hours prior to Screening may be used

units). eosinophils (in relative and absolute units); basophils (in relative and absolute units); monocytes (in relative and absolute units); lymphocytes (in relative and absolute units).			
---	--	--	--

Approximately 40 ml of blood will be drawn from the patient in this trial for laboratory tests to assess safety. The blood volume can be increased in case of need for additional laboratory studies to assess the dynamics of changes in the analysed indicators.

In the course of the trial, blood is taken from the patient for clinical and biochemical tests at the screening (Visit 0) and at Visits 2, 4; for serological tests for infections only at the screening (Visit 0) - according to the schedule of conducting test procedures.

During the trial, the patient's clinical urinalysis is performed on Visits 0, 2, 4.

The above standard laboratory tests for blood and urine will be performed in the local laboratory of the investigational site.

A rapid test for IgM antibodies to SARS-CoV-2 (blood collection for a qualitative test based on the immunochromatographic assay method) is performed at screening to avoid inclusion of patients with coronavirus infection (COVID- 19).

6.3.9. Compliance assessment

Compliance is assessed on the basis of records of dispensed/returned medication. The procedure is performed at visits 3 and 4 of the patient to the investigational site. Additionally, the assessment is conducted during telephone visits (calls) by interviewing the patient.

An acceptable compliance rate for this trial, based on a record of dispensed/returned medication, is considered to be 80-120%. If a patient is unresponsive to therapy, the investigator must assess the appropriateness of the patient's continued participation in the trial and decide whether to continue participation.

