5.3. Criteria for the exclusion of subjects

1. Withdrawal of informed consent by the patient and/or the patient's legal representative.
2. Need for additional therapy not permitted under this protocol.
3. Serious adverse events or adverse events that do not fulfil the criteria for seriousness and where, in the opinion of the investigator, further participation in the trial would be dangerous to the health or well-being of the patient.
4. Investigator or sponsor's decision to exclude a patient due to a significant protocol deviation/protocol violation.
5. Any patient condition that, in the reasonable judgement of the investigator, requires the

patient to be withdrawn from the trial.

6. Positive result of at least one of the following tests: blood tests for HIV, syphilis, hepatitis B and C, if the test results are obtained after the patient's randomization procedure.
7. Allergic reaction to trial medications requiring their cancellation.
8. Loss of contact with the patient followed by failure to attend the visit.
9. Recurrent stroke.
10. Positive result of the rapid test for IgM antibodies to SARS-CoV-2 virus and/or positive result of laboratory examination for the presence of SARS-CoV-2 RNA using nucleic acid amplification methods, regardless of clinical manifestations.
11. Diseases and/or conditions of the subject detected for the first time during routine medical examinations and procedures that prevent the subject from continuing his/her participation in the trial, and/or indicate that the patient was wrongly included in the trial (failure to meet the selection criteria for the trial at the time of inclusion).

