6.4. Restrictions of the trial

The Investigator will explain to the patient that the patient must abide by certain restrictions while participating in the trial. Such restrictions are also detailed in the Patient Information Sheet with Informed Consent Form.

Therapeutic regimen

In the present trial, the patient has the responsibility to comply with all recommendations of the investigating physician for primary and concomitant therapy and lifestyle.

Contraception

Prior to participation in the trial, all patients should be informed about the importance of preventing unwanted pregnancy during participation in the trial and the potential risk factors for unwanted pregnancy. The acceptable contraceptive methods considered in this trial are:

- non-hormonal IUD;
- condom with intravaginal spermicide;
- cervical caps with spermicide;
- diaphragm with spermicide.

A prerequisite for participation in this clinical trial is consent to use the contraceptive methods described above for the duration of the trial or complete abstinence from sexual activity for the duration of the trial.

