9.6. Population to be analysed

The following population groups will be used for the analyses:

1. The ITT (Intent-to-treat) population will include all randomized patients regardless of investigational product/placebo administration.
2. The mITT (modified Intent-to-treat) population will include patients who have completed the full course of therapy, regardless of the presence of Protocol violations/ deviations.
3. The PP (Per protocol) population will include patients who completed the trial in accordance with the Protocol.

At the stage of statistical data processing, additional analyses of the efficacy and/or safety of investigational product/placebo in subpopulations of patients of different age groups can be performed.

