11.8. Compliance with the Protocol

The Investigator shall conduct the trial in accordance with the approved Protocol.

A deviation from the Protocol is any change, inconsistency, or departure from the trial design or procedures of the Trial Protocol.

Any deviation from the Protocol during the conduct of a clinical trial must be recorded and reflected in the trial documentation.

All deviations from the Protocol are categorized into major deviations and minor deviations.

Minor deviation from the protocol - does not significantly affect the rights, safety and welfare of the patient or the completeness, accuracy and reliability of the trial data.

A significant protocol deviation (or protocol violation) is a deviation that may affect the rights, safety and welfare of the patient or the completeness, accuracy and reliability of the trial data.

Examples of significant deviations from protocol:

- patient met the exclusion criteria for the trial but was not excluded;
- patient has received a prohibited concomitant therapy drug;
- patient was included in the trial although he/she did not fulfil the selection criteria;
- performing trial procedures without obtaining written informed consent from the patient;
- violations of the procedure of IP administration by the patient (prescribing to one patient an IP with different randomization codes, inconsistency of labelling and randomization code in the source documentation, CRF, on all types of product packaging and in the patient registration and dispensing logs of the investigational product);
- patient indiscipline, failure to comply with restrictions during participation in the trial;
- systematic (repeated at least 2 times) negligent loss at a investigational site of data or samples collected for trial; and the negligent loss of data or samples collected for trial at a investigational site;
- skip of visits.

Major deviations must be reported to the ethics committee. If major deviations from the protocol are found, the patient should be excluded from the final analysis of efficacy data.

In the event that the visit procedures exceed the timeframes outlined in this protocol, the possibility of the patient's continued participation in the trial will be considered by the Sponsor, at the request of the investigator, on a case-by-case basis.

11.9.Final trial report

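### Protocol 6.3.9 makes lack of response to therapy, where non-compliance is evidently meant, the trigger for a mandatory review of continued participation, and leaves the 80-120% range with no stated action

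*Protocol*

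**What the plan says.** Protocol 6.3.9 covers drug accountability. Compliance is judged from dispensed and returned medication at Visits 3 and 4, with patient interviews at the two telephone visits. It then gives the range: "An acceptable compliance rate for this trial, based on a record of dispensed/returned medication, is considered to be 80-120"%. The sentence that follows directly is: "If a patient is unresponsive to therapy, the investigator must assess the appropriateness of the patient's continued participation in the trial". It ends by requiring the investigator to decide whether participation goes on.

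Other sections bear on non-adherence without mentioning the range:

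- Section 4.6 makes the investigator responsible for assessing compliance and, where possible, for finding out why it was not observed.
- Section 6.4, among the trial restrictions, says "the patient has the responsibility to comply with all recommendations of the investigating physician for primary and concomitant therapy".
- Section 11.8 lists among its examples of significant deviations "patient indiscipline, failure to comply with restrictions during participation in the trial", and states: "If major deviations from the protocol are found, the patient should be excluded from the final analysis of efficacy data".
- Section 5.3, criterion 4, allows removal on the "Investigator or sponsor's decision to exclude a patient due to a significant protocol" deviation or violation.
- Section 9.3 takes patients with significant deviations that may affect the efficacy assessment out of the PP population.

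Sections 9.6 and 9.7.2 make PP, the patients who completed the trial according to the protocol, the primary population, with ITT and mITT additional. On the second of these: "The mITT (modified Intent-to-treat) population will include patients who have completed the full course of therapy". SAP Section 11 repeats these definitions and sets no compliance threshold.

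**The concern.** This is an operative instruction to sites, and its trigger names a clinical outcome. A site following the words would review a stroke patient's participation because the patient is not improving, and could end it. That patient would not complete the course and would drop out of both PP and mITT. Membership of the primary analysis set could then depend partly on the outcome being analysed.

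The second half of the problem is the gap this leaves. The protocol states a numerical range for acceptable compliance, and the sentence placed to say what happens outside it speaks of something else. The range therefore has no action attached to it.

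**Working it through.** No sample size, power or alpha figure depends on this sentence, so the check is a comparison of texts. It asks which reading the protocol supports, and what each reading would do.

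**Which reading fits**

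1. *Heading and data source.* Everything before the sentence in 6.3.9 concerns medication counts and interviews about intake. Nothing in the section measures response.
2. *Preceding sentence.* It defines acceptable compliance. A rule for what to do when compliance is unacceptable is the natural continuation; a rule on clinical response is not.
3. *Section 4.6.* It already asks the investigator to follow up when compliance was not observed. A review of participation in 6.3.9 fits as the next step.
4. *Schedule.* Under 6.3.9 and Appendix 1, compliance is assessed at Telephone visit 1, Visit 3, Telephone visit 2 and Visit 4. Under 6.3.11, mRS and NIHSS are scored at Visits 0, 2 and 4, and MoCA, HADS and the Rivermead index at Visits 1, 2 and 4. So no efficacy scale is collected at Visit 3 or on the calls. Visit 4 has scales but is the end of therapy. Visit 2 has scales but no compliance assessment.
5. *Reasons for stopping.* Lack of response is not defined in the protocol, is not a named exclusion criterion in 5.3, and is not a named reason for discontinuation in 5.4.2. Only the open-ended entries could reach it: criterion 5 ("Any patient condition that, in the reasonable judgement of the investigator, requires the" patient's withdrawal) and the category of other reasons in 5.4.2.

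All five point to non-compliance as the intended trigger.

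**What each reading does**

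| | Literal: not responding | Intended: non-compliant |
|---|---|---|
| Trigger | Clinical outcome, undefined | Compliance outside 80-120% |
| Required action | Review and decision on participation | Review and decision on participation |
| If the patient is stopped | Leaves PP and mITT because of outcome | Leaves PP and mITT because of drug taking |
| Use of the 80-120% range | No stated action | Defined trigger |

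**Whether the range has an action elsewhere**

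Protocol 4.6, 5.3 (criterion 4), 6.4, 9.3 and 11.8 together give poor adherence a general consequence: it can be investigated, treated as a significant deviation, and lead to exclusion from the trial or from the efficacy analysis. None of them refers to 80-120%, and the SAP does not either.

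**The case against.** The strongest reply is that this is a slip of translation that context resolves. The English text has others: type I error appears as genus I error in Sections 9.1 and 9.8, and Section 2.2 gives an intravenous route for the tablets. If the context is as clear as argued above, an investigator is unlikely to misread the sentence, and the documents do not show that sites work from the English version. This stands as a reason for a low grade. It does not make the reviewed text right, because the sentence is an instruction with a mandatory verb.

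Non-compliance is also already handled in general terms in the sections listed above, and the list in 11.8 gives examples only, so it need not name a percentage. This too stands. What is missing is narrower: an action tied to the range that the protocol itself sets.

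Finally, the literal reading has little to work with, since no scale is collected at Visit 3 or on the calls. It requires a review and not removal, and criterion 5 in 5.3 already leaves the investigator discretion. An early-withdrawal visit with the content of Visit 4 (Sections 6.1 and 6.2) means mRS can still be obtained for ITT. All of this is correct.

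A reader might infer that the sentence orders withdrawal of non-responders, or that it biases the primary result. The documents support neither. The text asks for an assessment and a decision, and no rate of such discontinuations is given from which the size of a bias could be worked out.

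**Conclusion.** The trigger in 6.3.9 is wrong as written. It names lack of response where non-compliance is evidently meant. In consequence, an instruction on participation is tied to outcome, which could affect who belongs to the PP and mITT sets, and the 80-120% range has no stated action.

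That non-compliance was intended is an inference. It rests on the heading, the data source, the preceding sentence, Section 4.6, the schedule of scales, and the absence of any named non-response criterion. The literal reading is not impossible, because criterion 5 in 5.3 could accommodate it. No effect on the estimated difference or on power is claimed. If the text that sites actually use already says non-compliant, only the English version needs correcting; the documents do not settle this. Severity: minor.

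**What to change.** In Protocol 6.3.9, change the opening condition of the sentence to: If a patient is non-compliant (outside 80-120%). Leave the rest of the sentence, the required review and decision, as it is.

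The cost is one phrase, with no added patients, visits, data or analyses. Under Section 11.7, a change treated as affecting the conduct of the trial needs approval from the Ethics Council, the local ethics committees and the regulatory authorities, so it is best carried with the next amendment.
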